8.3.2. Method of Detecting Adverse Events and Serious Adverse Events

Care will be taken not to introduce bias when detecting adverse events or serious adverse events. Open-ended and nonleading verbal questioning of the participant is the preferred method to inquire about adverse event occurrence.

8.3.3. Follow-up of Adverse Events and Serious Adverse Events

The investigator is obligated to perform or arrange for the conduct of supplemental measurements and evaluations as medically indicated to elucidate the nature and causality of the adverse event, serious adverse event, or PQC as fully as possible. This may include additional laboratory tests or investigations, histopathological examinations, or consultation with other health care professionals.

Adverse events, including pregnancy, will be followed by the investigator as specified in Appendix 5, Adverse Events, Serious Adverse Events, Product Quality Complaints, and Other

Safety Reporting: Definitions and Procedures for Recording, Evaluating, Follow-up, and Reporting.

8.3.4. Pregnancy

All initial reports of pregnancy in female participants or partners of male participants must be reported to the sponsor by the study-site personnel within 24 hours of their knowledge of the event using the appropriate pregnancy notification form. Abnormal pregnancy outcomes (eg, spontaneous abortion, fetal death, stillbirth, congenital anomalies, ectopic pregnancy) are considered serious adverse events and must be reported using a serious adverse event reporting form. Any participant who becomes pregnant during the study must be promptly withdrawn from the study and discontinue further study intervention.

Follow-up information regarding the outcome of the pregnancy and any postnatal sequelae in the infant will be required.

8.3.5. Disease-Related Events and Disease-Related Outcomes Not Qualifying as Adverse Events or Serious Adverse Events

All events that meet the definition of a serious adverse event will be reported as serious adverse events, regardless of whether they are protocol-specific assessments.

8.3.6. Adverse Events of Special Interest

Clinically relevant intervention-emergent AEs of special interest will be summarized separately grouped in the following MedDRA based categories:

- **Sedation:** sedation; somnolence; altered state of consciousness; depressed level of consciousness; hypersomnia; stupor
- **Dissociation:** depersonalisation/derealisation disorder; derealisation; dissociative disorder; flashback; hallucination; hallucination, auditory; hallucination, visual; illusion; somatic hallucination; hyperacusis; tinnitus; diplopia; vision blurred; ocular discomfort; photophobia; visual impairment; dysaesthesia; oral dysaesthesia; paraesthesia; paraesthesia oral; pharyngeal paraesthesia; time perception altered; daydreaming; delusional perception; feeling hot; feeling cold; feeling of body temperature change
- **Suicidality:** completed suicide; depression suicidal; intentional overdose; intentional self-injury; multiple drug overdose intentional; poisoning deliberate; self-injurious behavior; self-injurious ideation; suicidal behavior; suicidal ideation; suicide attempt; toxicity to various agents
- Suggestive of abuse potential: aggression; confusional state; decreased activity; dependence; disorientation; dissociation; dissociative disorder; dizziness; drug abuse; drug abuser; drug dependence; drug use disorder; drug detoxification; drug diversion; drug rehabilitation; drug tolerance; drug tolerance increased; drug withdrawal convulsions; drug withdrawal headache; drug withdrawal syndrome; euphoric mood; feeling abnormal; feeling drunk; feeling of relaxation; hallucination; hallucination, auditory; hallucination, gustatory; hallucination, olfactory; hallucination, synaesthetic; hallucination, tactile; hallucination, visual; hallucinations, mixed; inappropriate affect; mental impairment; product tampering; psychomotor hyperactivity; psychotic disorder; rebound effect; somatic hallucination;

somnolence; substance abuser; substance dependence; substance use; substance use disorder; substance-induced mood disorder; substance-induced psychotic disorder; thinking abnormal; withdrawal arrhythmia; withdrawal syndrome

- Cystitis: adenoviral hemorrhagic cystitis; allergic cystitis; bladder candidiasis; bladder diverticulitis; cystitis bacterial; cystitis erosive; cystitis escherichia; cystitis glandularis; cystitis gonococcal; cystitis helminthic; cystitis hemorrhagic; cystitis interstitial; cystitis klebsiella; cystitis noninfective; cystitis pseudomonal; cystitis radiation; cystitis ulcerative; cystitis viral; emphysematous cystitis; eosinophilic cystitis; fungal cystitis; lupus cystitis; malacoplakia vesicae; schistosomiasis bladder; trigonitis; tuberculosis bladder; urinary bladder abscess; viral hemorrhagic cystitis
- **Hepatic impairment**: acquired complement deficiency disease; bilirubin excretion disorder; crigler-najjar syndrome; HELLP (hemolysis, elevated liver enzymes, and a low platelet count) syndrome; hepatic function abnormal; hyperammonemic crisis; hyperammonemia; hypertransaminasemia; hypoalbuminemia; hypoproteinemia

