1. PROTOCOL SUMMARY

1.1. Synopsis

Open-label Long-Term Extension Study for Participants With Treatment-Resistant Major Depressive Disorder Who are Continuing Esketamine Nasal Spray Treatment From Study 54135419TRD3013

Open-label Extension Study to Assess Long-term Safety of Esketamine Nasal Spray

Esketamine hydrochloride (HCl) is referred to as JNJ-54135419-AAC. Esketamine is a nonselective, noncompetitive antagonist of the N-methyl-D-aspartate receptor (NMDAR), an ionotropic glutamate receptor. Through NMDAR antagonism, esketamine produces a transient increase in glutamate release leading to increases in α-amino-3-hydroxy-5-methyl-4-isoxazole propionic acid receptor (AMPAR) stimulation and subsequently to increases in neurotrophic signaling that restore synaptic function in these mood regulatory brain regions. Esketamine nasal spray is indicated for use in combination with a selective serotonin reuptake inhibitor (SSRI)/ serotonin-norepinephrine reuptake inhibitor (SNRI) to treat adults with treatment-resistant major depressive disorder (MDD). Esketamine nasal spray has also been approved by the United States Food and Drug Administration for MDD with acute suicidal ideation or behavior.

OBJECTIVES AND ENDPOINTS

Primary

Objectives

Primary	
To assess the long-term safety and tolerability of esketamine nasal spray in combination with an SSRI/SNRI in participants who have completed 32 weeks of esketamine nasal spray treatment in Study TRD3013.	Intervention-emergent adverse events (AEs), including intervention-emergent AEs of special interest Suicidal ideation and behavior: Columbia-Suicide Severity Rating Scale (C-SSRS)
Secondary	

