5.3. Primary Endpoint(s) Analysis

The primary analysis will be based on the Efficacy analysis set which will be same as Safety analysis set (due to design of the study) using the safety data collected during both Study 54135419TRD3013 and Study 54135419TRD4010.

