5.3.1. Definition

The two primary endpoints are treatment-emergent adverse events, and Suicidal ideation and behavior: Columbia-Suicide Severity Rating Scale (C-SSRS).

Note: although the protocol lists intervention-emergent adverse events as a primary endpoint, here the terminology treatment-emergent adverse events will be applied.

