5.3.2. Estimand for treatment-emergent adverse events

Primary Trial Objective: To assess the long-term safety and tolerability of esketamine nasal spray in combination with an SSRI/SNRI in participants who have completed 32 weeks of esketamine nasal spray treatment in Study 54135419TRD3013.

Estimand Scientific Question of Interest: What is the safety and tolerability of esketamine nasal spray in combination with an SSRI/SNRI in participants who have completed 32 weeks of esketamine nasal spray treatment in Study 54135419TRD3013, based on the development of treatment-emergent adverse events (AEs)?

The estimand is defined by the following 5 components:

Study Intervention: esketamine nasal spray in combination with an SSRI/SNRI

Population: participants who have completed 32 weeks of esketamine nasal spray treatment in Study 54135419TRD3013 and received at least one dose of esketamine in Study 54135419TRD4010

Variable: development of treatment-emergent AE: from the initial administration of study intervention in Study 54135419TRD3013 through the day of last dose in Study 54135419TRD4010 plus 30 days

Summary Measure: number and incidence of subjects who develop an treatment-emergent AE per person-time at risk

Intercurrent events and their corresponding strategies:

	Name of Strategy for Addressing Intercurrent
Intercurrent Events	Events and Its Description
	While on treatment: All AEs occurring through
intervention for any reason	the day of last dose plus 30 days are included in
	analysis
Withdrawal from the study	While on treatment: Same as above

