6.7. Appendix 7: Adverse Events of Special Interest

Adverse events of special interest are defined as follows:

AE Special Interest Category	Preferred Term
Sedation	sedation
Sedation	somnolence
Sedation	altered state of consciousness
Sedation	depressed level of
	consciousness
Sedation	hypersomnia
Sedation	stupor

AE Special Interest Category	Preferred Term
Dissociation	depersonalisation/derealisation disorder
Dissociation	derealisation
Dissociation	dissociative disorder
Dissociation	flashback
Dissociation	hallucination
Dissociation	hallucination, auditory
Dissociation	hallucination, visual
Dissociation	illusion
Dissociation	somatic hallucination
Dissociation	hyperacusis
Dissociation	tinnitus
Dissociation	diplopia
Dissociation	vision blurred
Dissociation	ocular discomfort
Dissociation	photophobia
Dissociation	visual impairment
Dissociation	dysaesthesia
Dissociation	oral dysaesthesia
Dissociation	paraesthesia
Dissociation	paraesthesia oral
Dissociation	pharyngeal paraesthesia
Dissociation	time perception altered
Dissociation	daydreaming
Dissociation	delusional perception
Dissociation	feeling hot
Dissociation	feeling cold
Dissociation	feeling of body temperature change

AE Special Interest Category	Preferred Term
Suicidality	completed suicide
Suicidality	depression suicidal
Suicidality	intentional overdose
Suicidality	intentional self-injury
Suicidality	multiple drug overdose intentional
Suicidality	poisoning deliberate
Suicidality	self-injurious behavior
Suicidality	self-injurious ideation
Suicidality	suicidal behavior
Suicidality	suicidal ideation
Suicidality	suicide attempt
Suicidality	toxicity to various agents

CONFIDENTIAL – FOIA Exemptions Apply in U.S.

AE Special Interest Category	Preferred Term
Suggestive of abuse potential	aggression
Suggestive of abuse potential	confusional state
Suggestive of abuse potential	decreased activity
Suggestive of abuse potential	dependence
Suggestive of abuse potential	disorientation
Suggestive of abuse potential	dissociation
Suggestive of abuse potential	dissociative disorder
Suggestive of abuse potential	dizziness
Suggestive of abuse potential	drug abuse
Suggestive of abuse potential	drug abuser
Suggestive of abuse potential	drug dependence
Suggestive of abuse potential	drug use disorder
Suggestive of abuse potential	drug detoxification
Suggestive of abuse potential	drug diversion
Suggestive of abuse potential	drug rehabilitation
Suggestive of abuse potential	drug tolerance

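### The Dissociation special-interest list leaves out the term 'dissociation', so participants whose only dissociative event carries that code are not counted in the category

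*Protocol*

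**What the plan says.** Protocol 8.3.6 sorts special-interest adverse events into six categories, each defined by a list of terms. The Dissociation list begins "depersonalisation/derealisation disorder; derealisation; dissociative disorder; flashback; hallucination; hallucination, auditory; hallucination, visual; illusion" and continues to 27 entries, ending with temperature sensations. It is not marked as a set of examples, and no rule is given for adding terms. SAP Appendix 7 repeats the lists as a table of preferred terms introduced by "Adverse events of special interest are defined as follows". SAP 5.3.2.1.1 refers to that table for the content of each category when incidence is summarised.

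The term *dissociation* appears in both documents under abuse potential. In the protocol it sits in the run "dependence; disorientation; dissociation; dissociative disorder; dizziness; drug abuse".

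The protocol synopsis includes special-interest events in the primary endpoint: "Intervention-emergent adverse events (AEs), including intervention-emergent AEs of special interest". The SAP is narrower. Section 5.3.1 states "The two primary endpoints are treatment-emergent adverse events, and Suicidal ideation and behavior: Columbia-Suicide Severity Rating Scale (C-SSRS"), and the estimand in 5.3.2 has "Variable: development of treatment-emergent AE: from the initial administration of study intervention in Study 54135419TRD3013" as the start of its variable, with no mention of special-interest categories. The main safety analysis is run "using the safety data collected during both Study 54135419TRD3013 and Study 54135419TRD4010". SAP 5.3.2.1.3 repeats the special-interest summary for events starting in the extension.

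**The concern.** A table row headed Dissociation would exclude events coded as *dissociation* while including peripheral terms such as tinnitus, feeling hot and ocular discomfort. The missing term is a common one for this drug. Protocol 2.2.3.4 names it among the events reported by at least 10% of esketamine participants in the short-term studies.

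The grouped row also matters more in this study than in earlier ones. Protocol 2.2.3.4 describes dissociative symptoms in the earlier programme using a dedicated scale (the CADSS). The Schedule of Activities here contains no such scale, so dissociation in the extension is captured only through adverse event reports. The category incidence is the planned summary of those reports, and a reader who sees only that row could take the rate to be lower than it is.

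**Working it through.** **Step 1: compare the lists.**

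| Check | Protocol 8.3.6 | SAP Appendix 7 |
|---|---|---|
| Terms under Dissociation | 27 | 27, the same set |
| *dissociation* under Dissociation | absent | absent |
| *dissociation* under abuse potential | present (49 terms in that list) | present |
| *dissociative disorder* as its own entry | present in both categories | present in both categories |

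The two documents set the lists out differently, one as running text and one as a table, and they agree. A fault in reading the PDF is therefore not a plausible explanation. Because *dissociation* and *dissociative disorder* are separate neighbouring entries under abuse potential, the plan itself treats them as different terms.

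**Step 2: look for a rule that would explain the omission.** A rule of one category per term would do so, but the lists do not follow one. Five Dissociation terms also appear under abuse potential: *dissociative disorder*; *hallucination*; *hallucination, auditory*; *hallucination, visual*; *somatic hallucination*. The Sedation list, "sedation; somnolence; altered state of consciousness; depressed level of consciousness; hypersomnia; stupor", shares *somnolence* with abuse potential. Neither document states a reason.

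**Step 3: trace the outputs.**

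- Affected: the Dissociation category incidence over both studies (SAP 5.3.2.1.1) and its extension-only repeat (SAP 5.3.2.1.3).
- Not affected: overall treatment-emergent totals, per-term tables, the abuse-potential category and the C-SSRS analyses.
- Recoverable: the special-interest listing in SAP 5.3.2.1.1 still shows these participants, because the term qualifies through abuse potential.

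**Step 4: illustrate the size.** The plan gives no figure to reproduce. Let N be the number of participants, p the proportion with *dissociation*, and q the share of those who also have at least one of the 27 listed terms. Then

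missed participants = N × p × (1 − q), and the shortfall in the category proportion = p × (1 − q).

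N = 100 to 200 is the expected enrolment in Protocol 9.2. The documents give neither p nor q for this population, so both are assumptions.

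| p | q | Missed, N = 100 | Missed, N = 200 | Shortfall (percentage points) |
|---|---|---|---|---|
| 5% | 0% | 5 | 10 | 5 |
| 5% | 50% | 2.5 | 5 | 2.5 |
| 10% | 0% | 10 | 20 | 10 |
| 10% | 50% | 5 | 10 | 5 |
| 10% | 80% | 2 | 4 | 2 |
| 30% | 0% | 30 | 60 | 30 |
| 30% | 50% | 15 | 30 | 15 |
| any | 100% | 0 | 0 | 0 |

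For example, 200 × 0.10 × (1 − 0.50) = 10. Overlap could be substantial, since paraesthesia is one of the 27 terms and Protocol 2.2.3.4 also names it as common. For the extension-only repeat, Protocol 2.3 says dissociation becomes less frequent with continued dosing, which points to a smaller p.

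**The case against.** The strongest case on the other side has four parts.

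**Category names are usually absent from their own lists.** Only Sedation, of the six categories, contains its name as a term. Cystitis has no bare *cystitis*, and Hepatic impairment, Suicidality and abuse potential also lack theirs. This is correct, so the contrast with Sedation carries little weight. The point rests instead on *dissociation* being a listed preferred term elsewhere in the same appendix, with double listing permitted.

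**The omission may be inherited and deliberate.** The SAP version history cites alignment with the parent study's SAP for other changes, and the data are pooled with that study. If the parent used the same list, leaving it alone keeps the two reports comparable. The parent list cannot be seen here, so this remains possible. Calling the figure too low does presume that the term belongs in the category. The plan states no reason for leaving it out, and a reader of the table would expect it to be included.

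**The size is unknown, and 10% is not a ceiling.** Protocol 2.2.3.4 gives 10% as a reporting threshold, so the short-term rate was at least that. The main analysis also includes the parent study, where early dosing took place. This stands. The table above therefore goes to 30%, and none of its rows bounds the effect.

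**Little depends on one grouped row.** The rate for the term itself is reported, the listing shows the participants, and no hypothesis is tested. This is true and limits the priority. It does not make the row correct.

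**Conclusion.** The point holds. As written, the Dissociation category excludes participants whose only dissociative event codes to *dissociation*. If the term belongs in the category, the reported proportion is either unchanged, when every such participant also has another listed term, or too low. Only the direction can be settled from the documents. The shortfall is 0 to 10 percentage points at an assumed 10% rate, and larger if the rate is higher. The effect is confined to the category summaries. It leaves the SAP's primary endpoints and estimand untouched, although the protocol does name special-interest events within its primary endpoint. It should be fixed because it affects a prespecified safety output and costs almost nothing to correct.

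**What to change.** Add *dissociation* to the Dissociation list in SAP Appendix 7 before database lock, and keep it under abuse potential; the list goes from 27 to 28 terms. Record the change in SAP Appendix 2, which at present contains only the decision not to run an interim analysis. Align Protocol 8.3.6 at the next formal amendment, which Protocol 10.3.1 requires for any change to the protocol.

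If the exclusion is intended, or carried over from the parent study, state the reason and report the category with and without the term. Showing both also covers the case where the corrected figure no longer matches the parent study's. The documents give no lock date. If lock has already passed, the additional SAPs allowed for in the SAP introduction provide a route for a supplementary table.

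The cost is one row in a look-up list, one entry in Appendix 2, and a category figure that stays the same or becomes less favourable. No new data are needed.

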2.2.3.4. Safety Studies

In 6 completed Phase 2 and 3 studies in TRD as of 04 March 2020 (TRD2003, TRD3001, TRD3002, TRD3005, TRD3003, and TRD3004), a total of 1,708 participants received esketamine (611 patient-years of exposure) and 486 participants received placebo (107 patient-years of exposure). Study TRD2005 was completed after this cutoff date; in this study an additional 122 participants received at least 1 dose of esketamine nasal spray for a median duration of exposure of 24 to 25 days across the 3 dose groups (28 mg, 56 mg, and 84 mg). In one of the ongoing studies (open-label Phase 3 extension safety study TRD3008), 1,148 participants have received at least 1 dose of esketamine for a median duration of exposure (including exposure in previous controlled trials) of 143 weeks through 20 May 2020; 991 participants had at least 12 months of exposure, and 850 participants had at least 24 months of exposure.

- Over the therapeutic dose range for use in a TRD population (28 to 84 mg), most intervention-emergent adverse events (AEs) with esketamine were mild to moderate in severity, occurred shortly after dosing, were transient, and resolved the same day.
- In the short-term TRD studies, the most common intervention-emergent AEs (reported by ≥10% of participants who received esketamine in combination with a newly initiated SSRI/SNRI and observed more frequently compared with participants who received placebo in combination with a newly initiated SSRI/SNRI) were nausea, dissociation, dizziness, vertigo, headache, dysgeusia, somnolence, paresthesia, hypoesthesia, and hypoesthesia oral in Studies TRD3001 and TRD3002, and dizziness, nausea, headache, fatigue, blood pressure increased, dissociation, and vertigo in Study TRD3005.
- Across the Phase 3 studies in TRD, esketamine had a consistent, well-characterized, and tolerable safety profile. Most reported intervention-emergent AEs during induction and maintenance esketamine treatment, including those that were most common, were reported postdose on the day of dosing and resolved the same day. Only a minority of the reported intervention-emergent AEs were assessed as severe. There were no new intervention-emergent AEs considered associated with the use of esketamine reported with longer-term repeated dosing of esketamine in combination with a newly initiated SSRI/SNRI of up to 1 year.

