- Among the 1,708 participants treated with esketamine across the completed Phase 2 and 3 studies in TRD, there were 4 deaths, including 2 completed suicides. Through 04 March 2020, in the ongoing long-term open-label safety extension Phase 3 study (TRD3008, 1,148 participants), 3 deaths (completed suicide, myocardial infarction, and death due to multiple injuries from car accident) were reported in esketamine-treated participants.
- Discontinuation of esketamine treatment due to intervention-emergent AEs was uncommon across all clinical studies and tended to be highest early in the course of treatment. With long-term treatment of up to 1 year, <10% of treated participants in the open-label long-term safety study (TRD3004) experienced intervention-emergent AEs that necessitated discontinuation of esketamine.

- Overall, across Phase 2 and 3 TRD studies, suicidality-related events were reported at a frequency of ~1% to 5%, and most of the reported cases were those of suicidal ideation. Severe suicidality-related intervention-emergent AEs were reported at a low incidence (<1% for individual preferred terms) in each of the Phase 2 and 3 studies. Clinical review of suicidality-related intervention-emergent AEs indicated that most of these events were likely associated with the underlying disease.
- The most common psychological effects of esketamine have been transient dissociative/perceptual changes (including distortion of time and space and illusions), derealization and depersonalization. The majority of participants who were administered esketamine experienced dissociative symptoms as assessed by the Clinician-Administered Dissociative States Scale (CADSS). The symptoms peaked at around 40 minutes from the time of esketamine nasal spray administration and typically resolved by 1.5 to 2 hours after dosing. The severity of dissociative symptoms tended to reduce over time with repeated treatments. Dissociation reported as severe in intensity at the incidence of less than 4% across studies, was not considered serious for any participants in completed Phase 2 and 3 studies, and infrequently led to discontinuation of study intervention. Transient dissociative/perceptual changes (based on the CADSS scores, the overall intervention-emergent AE incidence rates, and the severe intervention-emergent AE incidence rates) were more pronounced in participants receiving the esketamine 84 mg dose than in those receiving the esketamine 56 mg dose.

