2.3. Benefit-Risk Assessment

A structured approach was applied to the selection and analysis of all the endpoints in the Phase 3 esketamine program in TRD that have an important effect on the benefit-risk balance. Proportions of beneficial events were compared to proportions of harmful events. While some of the dichotomous endpoints (remission and response rates) that underlay these comparisons are not associated with formal statistical testing, they do characterize clinically significant differences and provide an overall picture of the benefit-risk balance for esketamine. More detailed information about the known and expected benefits and risks of esketamine nasal spray may be found in the IB (IB 2020).

The totality of evidence supports a positive benefit-risk balance for esketamine nasal spray as a new treatment for adults with TRD. The extensive clinical study program for esketamine in TRD demonstrates the rapid, robust, and sustained efficacy for improving depression symptoms in this difficult-to-treat population. Benefit-risk assessments estimate that between 6 and 18 more patients per 100 treated achieve remission of depression symptoms after 4 weeks of treatment with esketamine in combination with a newly initiated SSRI/SNRI compared to initiating treatment with an SSRI/SNRI alone. Further, once remission has been achieved on esketamine, continued maintenance treatment with esketamine nasal spray in combination with an SSRI/SNRI is estimated to result in 19 to 32 fewer relapses per 100 patients relative to those who discontinue esketamine. The safety experience with esketamine nasal spray indicated that most of the adverse reactions seen with the drug, including those of common events such as dissociative symptoms, dizziness/vertigo, increased blood pressure, and sedation, occur shortly after dosing while the patient is under the supervision of a health care provider, and resolve the same day. In addition, certain AEs such as dissociation, dizziness/vertigo, and nausea/vomiting tend to lessen in frequency with continued dosing.

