9.4.5. Safety Analyses

All safety analyses will be made on the Safety/Efficacy Population.

Adverse Events

The verbatim terms used in the eCRF by investigators to identify adverse events will be coded using the Medical Dictionary for Regulatory Activities (MedDRA). Any AE occurring at or after the initial administration of study intervention through the day of last dose plus 30 days is considered to be intervention-emergent. All reported intervention-emergent adverse events will be included in the analysis. For each adverse event, the percentage of participants who experience at least 1 occurrence of the given event will be summarized.

Intervention-emergent AEs of special interest will be summarized separately grouped in the categories as described in Section 8.3.6.

Summaries, listings, or participant narratives may be provided, as appropriate, for those participants who die, who discontinue intervention due to an adverse event, or who experience a serious adverse event.

Clinical Laboratory Tests

Only clinically relevant changes in laboratory parameters that meet the definition of an AE during the study are reported by the investigator as AEs and these will be included in the all intervention-emergent AE analyses.

Vital Signs

Descriptive statistics of pulse/heart rate, respiratory rate, and supine blood pressure (SBP and DBP) values and changes from Study TRD3013 baseline will be summarized at each scheduled time point. The percentage of participants with values beyond clinically important limits will be summarized.

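### The preferred term 'dissociation' is missing from the Dissociation category of adverse events of special interest and sits only under abuse potential, so the Dissociation result is undercounted

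*Protocol*

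**What the plan says.** The primary endpoint is intervention-emergent adverse events, "including intervention-emergent AEs of special interest" (protocol 1.1, repeated in section 3). Protocol 9.4.5 sets the grouping: "Intervention-emergent AEs of special interest will be summarized separately grouped in the categories as described in Section 8.3.6".

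Protocol 8.3.6 then gives the terms in each category. The Dissociation list opens with "depersonalisation/derealisation disorder; derealisation; dissociative disorder; flashback; hallucination; hallucination, auditory; hallucination, visual; illusion; somatic hallucination", continues through perceptual, visual, sensory and temperature terms, and ends without 'dissociation'. The abuse-potential list in the same section contains "dependence; disorientation; dissociation; dissociative disorder; dizziness; drug abuse".

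SAP Appendix 7 repeats these lists as a two-column table of category against preferred term, introduced by "Adverse events of special interest are defined as follows". SAP 5.3.2.1.1 points to that appendix for the AESI summary. SAP 5.3.2.1.3 repeats the AESI output for events that start in TRD4010.

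**The concern.** A programmer who follows Appendix 7 row by row will assign an event coded 'dissociation' to abuse potential and nowhere else. The category named after the drug's best-known psychological effect would then leave out the term that carries that name.

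The sponsor's own background text shows that the term matters. Protocol 2.2.3.4 states: "The most common psychological effects of esketamine have been transient dissociative/perceptual changes". It also lists the events reported by at least 10% of esketamine participants. For the older-adult short-term study it gives "dizziness, nausea, headache, fatigue, blood pressure increased, dissociation, and vertigo in Study TRD3005", and 'dissociation' is in the corresponding list for TRD3001 and TRD3002. Protocol 2.3 adds that "certain AEs such as dissociation, dizziness/vertigo, and nausea/vomiting tend to lessen in frequency with continued dosing". The primary analysis counts events from the first TRD3013 dose, so it includes early treatment.

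The TRD4010 Schedule of Activities (protocol 1.3) contains no dissociation scale. In the extension, dissociation is therefore captured through adverse event reports, and the AESI table is its dedicated summary.

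**Working it through.** **Step 1: list membership.** Counted from protocol 8.3.6; SAP Appendix 7 agrees on where the term is placed.

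| Category | Terms | Contains 'dissociation'? |
|---|---|---|
| Sedation | 6 | No (it does list 'sedation') |
| Dissociation | 27 | No |
| Suggestive of abuse potential | 49 | Yes |

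The protocol's running list and the SAP's row-by-row table agree, so damage from reading the PDF is very unlikely.

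**Step 2: does a rule explain the omission?**
- *One category per term?* No. Five terms are in both Dissociation and abuse potential: dissociative disorder; hallucination; hallucination, auditory; hallucination, visual; somatic hallucination. 'Somnolence' is in both Sedation and abuse potential.
- *A deliberately narrow category?* Implausible. The Dissociation list includes tinnitus, photophobia, feeling hot and daydreaming.
- *Category name included by implication?* Neither document says so, and Sedation lists its own name explicitly.

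**Step 3: direction.** Leaving out a term can only lower the category's participant count and proportion. Under SAP 5.3.2.1.1, time at risk stops at the first event, or else runs to last dose plus 30 days. A missed participant therefore leaves the numerator of an incidence rate and usually adds time to its denominator, which lowers the rate further.

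**Step 4: size.** The plan gives no figure to reproduce. Let
- N = 100 to 200, the expected enrolment (protocol 9.2);
- p = share with an event coded 'dissociation'. The anchor is 10%, because protocol 2.2.3.4 gives at least 10% in the short-term studies; the range of 10% to 30% is assumed;
- s = share of those who also have another listed Dissociation term. This is not in the documents; 50% is assumed, with a range of 0% to 75%.

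Participants missed = N × p × (1 − s).

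| p | s | Missed, N = 100 | Missed, N = 200 | Percentage points |
|---|---|---|---|---|
| 10% | 75% | 2.5 | 5 | 2.5 |
| 10% | 50% | 5 | 10 | 5 |
| 30% | 0% | 30 | 60 | 30 |

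**Step 5: effect on a reported figure (illustration).** Suppose 40 of 200 participants truly have a dissociative event: 20.0%, 95% Clopper-Pearson interval 14.7 to 26.2. With 10 missed, the table shows 30 of 200: 15.0%, interval 10.4 to 20.7.

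**Step 6: chance of missing anyone.** At the low end of the assumed range (2.5%), this is 1 − 0.975^100 = 0.920 at N = 100 and 1 − 0.975^200 = 0.994 at N = 200. With more overlap, s = 90%, the missed share is 10% × 0.10 = 1%, and the chance at N = 100 is 1 − 0.99^100 = 0.634.

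**The case against.** **The heading may be meant to count.** The Cystitis list has no plain 'cystitis' and the Hepatic impairment list has no 'hepatic impairment', so the lists might be read as additions to the category name. No text states that rule, and listing 'sedation' under Sedation contradicts it. If it was intended, the plan is ambiguous on part of the primary endpoint and the same edit resolves it. What stands is that the other categories deserve the same check.

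**Nothing is lost from the report.** SAP 5.3.2.1.1 gives the number, proportion and incidence rate for each adverse event, so 'dissociation' has its own row. It also appears in the AESI listing through abuse potential. The study is single-arm with no hypothesis, and no decision rule uses the Dissociation subtotal. All of this is true and limits the seriousness. It does not correct the Dissociation figure: separate term rows cannot be added to a participant count, because one participant may have several terms.

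**The size is mostly assumed.** This also stands. The 10% comes from short-term studies with a newly started antidepressant, whereas these participants completed 32 weeks and were judged to be benefiting, so 10% is not a floor here. The 30% has no source in the documents. Having no other listed term (s = 0) is an extreme, since paraesthesia is itself a listed Dissociation term and was reported in at least 10% in TRD3001 and TRD3002. The TRD4010-only table should be affected less, because dissociation lessens with continued dosing; no figure for it can be derived.

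**Conclusion.** The concern holds. As written, both documents leave the core term out of the Dissociation category, and the AESI summary built from them will undercount that category whenever a participant has 'dissociation' and no other listed Dissociation term. The omission and its direction are certain from the text.

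The amount is not. About 5 percentage points (5 of 100 or 10 of 200 participants) is a working figure that rests on p = 10% and s = 50%. The range of 2.5 to 30 points reflects assumed limits, and more overlap than 75% would make the loss smaller still. The overall adverse event result does not change. This should be corrected, but it does not threaten the study's main conclusions.

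**What to change.** Add 'dissociation' to the Dissociation category in SAP Appendix 7 before database lock, taking the list from 27 to 28 terms. Keep it under abuse potential too, as is already done for 'dissociative disorder' and 'somnolence'. Record it in SAP Appendix 2 as a change to protocol 8.3.6. While editing, confirm whether plain 'cystitis' was meant to be left out of its category.

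The cost is one row in an appendix and one line in the change record, with no new data and no new table. The drawback is comparability: if earlier esketamine reports used the same list, the new Dissociation figure will not match them directly. Showing the figure once more without the added term would deal with that.
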